
injury or if it is a signature of ongoing neuronal rearrangement and healing that occurs at the site of the injury.

Specific Aim 1: To detect the loci of injury in Veterans with mTBI and assess the mechanisms underlying functional neuroimaging changes related to IASIS treatment, and for a subset of Veterans with remaining symptoms, additional Nexalin treatment, using rs-MEG slow-wave source imaging. Our voxel-wise rs-MEG source-imaging technique will be used to identify abnormal slow-wave generation (delta band) in the baseline and post-treatment MEG exams to assess treatment-related changes on a single-subject basis. Healthy control (HC) Veterans, matched for combat exposure, will be used to establish an MEG normative database. Test-retest reliability of MEG slow-wave source imaging for mTBI will also be examined.

Hypothesis 1: Veterans with mTBI will generate abnormal MEG slow-waves during the baseline MEG exam. Voxel-wise MEG slow-wave source imaging will show significantly higher sensitivity than conventional MRI in identifying the loci of injury on a single-subject basis. The test-retest reliability of MEG slow-wave source imaging is expected to be high, with intra-class correlation coefficient (ICC) ≥ 0.75 between two sequential MEG exams.

Hypothesis 2: In wakefulness, slow-wave generation is a signature of ongoing neural rearrangement/healing, rather than a negative consequence of neuronal injury. IASIS treatment will enhance neural rearrangement/healing by initially potentiating slow-wave generation immediately after each treatment session.

Hypothesis 3: IASIS will ultimately reduce abnormal MEG slow-wave generation in mTBI by the end of the treatment course, owing to the accomplishment of neural rearrangement / healing. In Veterans with mTBI who finish IASIS treatment, but not in the sham group, MEG source imaging will show a significant decrease in abnormal slow-waves at post-treatment exam. Such significant decreases will also be evident in both the voxel-wise and overall abnormal MEG slow-wave measures.

Specific Aim 2: To examine treatment-related changes in PCS and PTSD symptoms in Veterans with mTBI. PCS and PTSD symptoms will be assessed at the baseline and post-treatment follow-up visits.

Hypothesis 4: Compared with the sham group, mTBI Veterans in the IASIS treatment group will show significantly greater decreases in PCS symptoms between baseline and post-treatment assessments.

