Neurophysiological studies in animals have established a solid connection between pathological delta-wave (1-4 Hz) generation in GM and injuries in WM. Polymorphic delta-band slowwaves produced by WM axonal lesions in cats were localized to the GM of cortex overlying the lesion [10,11]. Abnormal delta-waves can also be induced by the administration of atropine in the white matter (WM) [12]. It is known that atropine is a competitive antagonist of acetylcholine (ACh) receptors and can block and/or limit ACh. These animal experiments concluded that cortical deafferentation was a key factor in abnormal delta-wave production, owing to WM lesions (i.e., axonal injury) and/or blockages/limitations in the cholinergic pathway [60]. They also demonstrated that abnormal delta-waves can directly result from axonal and/or cholinergic blockage/limitation. Delta-wave-based measurements, such as rs-MEG slow-wave imaging, may be particularly sensitive to both mechanisms, which are two major contributing factors in TBI (Section B.1).

Slow-wave generation during non-REM sleep: Sleep studies further support the relationship between delta-wave generation and cholinergic blockage/limitation. During REM sleep and awake stages, the brain rhythms are dominated by oscillations at a frequency higher than delta waves. However during non-REM sleep stages 3 and 4, delta-waves are the dominant brain rhythm in the brain. ACh is one of the leading neurotransmitters related to sleep. ACh neurotransmitter affects certain cholinergic neurons that are active strongly during periods of REM sleep, but much less so during non-REM sleep and therefore are called REMON cells [61]. The marked reduction/limitation of

ACh release during the non-REM sleep stages 3 and 4 is a key contributor to the pronounced generation of delta waves during those stages [13].

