Fig. 5 shows preliminary data from a HC subject who participated in one session of IASIS. Three MEG exams were performed: the first right-before IASIS, the second immediately after IASIS (i.e., within a few minutes), and the third 96 hours after IASIS, all during wakefulness. The left panel of Fig. 5 shows a typical train of IASIS pulses at 3.6 Hz repetition rate (see Section D.4.1). The right panel shows that no abnormal MEG slow-waves (delta-wave band) were detected in either the MEG exam before IASIS and 96 hours after, which would be expected for a HC subject. However, immediately after IASIS, above threshold MEG slow-waves were detected from mid-line precuneous, mid-line vmPFC, bilateral medial temporal near hippocampus and amygdala, left insular, and cerebellum. These areas closely match the known brain networks observed during delta-wave sleep [83,84]. Due to strong artifacts from the IASIS device (left panel), we cannot obtain meaningful MEG slow-wave images during the IASIS session. However, we believe that the potentiation of slow-waves started during the IASIS session.

These preliminary data suggest that immediately after an IASIS treatment session, MEG slow-waves are potentiated in the same brain networks of delta-wave sleep, which supports Aim 1 and Hypothesis 2. **Figure 5 - See attached document.**

C.6 Ultimate Reduction of PCS and Abnormal MEG Slow-waves Post IASIS Treatment Course in mTBI

We performed a pilot study to assess the ultimate changes in MEG slow-waves and PCS in 6 individuals with chronic mTBI who went through the IASIS treatment course. IASIS treatments were applied twice weekly for 6 weeks, with MEG exams and PCS assessments at baseline and follow-up. None of the individuals from this pilot study had adverse events or noted side-effects.

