MEG data acquisition: rs-MEG data will be measured in alert condition using our Elekta-Neuromag VectorView MEG system. The entire recording will have three 5-minute blocks with eyes closed and a 60 sec break with eyes-open between each block. The participant will be instructed to keep the eyes closed and empty his/her mind while staying alert (see [1]). Data will be sampled at 1000 Hz. Eye blinks, eye movements, and

heart signals will be monitored. Three minutes of empty-room data will also be acquired to assess the sensor and environment noises. Precautions are taken to ensure head stability and minimize head movements (< 3 mm) (see [1]). We focus on eyes-closed rs-MEG data since low-magnitude eye-related artifacts can be easily removed, whereas eyes-open rs-MEG data are often contaminated by eye-blanks and strong eye-movement artifacts that cannot be fully removed without substantially diminishing the brain signals.

Conventional MRI and the construction of the BEM: Using a 3T GE Discovery MR750 MRI scanner, we will acquire a high-resolution MRI volume with a resolution of 1 1 1 mm³ using a T1-weighted 3D-IRSPGR pulse sequence. Gradient nonlinearity spatial distortion in MRI will be corrected using software developed by our collaborator, [name] lab [22]. The T1-weighted images will be used to construct a source grid for Fast VESTAL and a boundary element method (BEM) model for MEG forward calculation [101]. BEM mesh is constructed by tessellating the inner skull surface from the T1-weighted MRI into ~6000 triangular elements with ~5 mm size. Cubic source grid with 5 mm size and ~10,000 nodes covering the whole brain is used to calculate the MEG gain (i.e., lead-field) matrix. Conventional MRI sequences for identifying mTBI lesions in Veterans will also be performed: 1) Oblique T2*-weighted; 2) Oblique T2-weighted with ASSET; 3) Oblique FLAIR; 4) Oblique DWI. Susceptibility-weighted imaging will also be performed to detect subtle blood products.

D.3 Detecting mTBI using Voxel-wise MEG Slow-wave Source Imaging and Conventional MRI (Aim 1)

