D.3.1. MEG source imaging procedure for slow-waves: Eyes-closed rs-MEG data is first run through MaxFilter [102] to remove external interferences (e.g., artifacts due to metal objects, strong cardiac signals, environment noises, etc.), and to correct head movement. Next, residual artifacts due to micro eye-blanks, eye movements, and residual cardiac signals are removed using Independent Component Analysis using ICALAB (Riken, Japan). Here, the 2nd and 3rd 5-minute rs-MEG sensor-waveform datasets are registered to the 1st 5- minute dataset using MaxFilter. The artifact-free, eyes-closed, rs-MEG sensor-waveform datasets are divided into 2.5 second epochs. The data in each epoch are first DC-corrected and then run through a 1-4 Hz bandpass filter. Sensor-waveform covariance matrices are calculated for individual epochs after the band-pass filtering; then, the final sensor-waveform covariance matrix is obtained by averaging the covariance matrices across individual epochs for the total 15-minute data. Using such a covariance matrix, voxel-wise MEG slowwave source magnitude images are obtained for each participant following the Fast-VESTAL procedure [65].

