D.4.3. IASIS's immediate effect of slow-wave potentiation -- pre- and post-session rs-MEG changes: To achieve this goal, we will perform three pairs of pre- and post-session rs-MEG exams at the beginning, midpoint, and the end of the IASIS treatment course: in Visit 3 for the 1st IASIS session (S1), Visit 9 for the 7th IASIS session (S7), and Visit 14 for the 12th IASIS session (S12). The post-treatment rs-MEG will be performed within 30 minutes immediately after the treatment session. Two-factor mixed-design repeated measures ANOVA with covariates, equivalent to linear mixed effect model, will be applied for statistical analysis. We will: 1) assess the within-subject significance of the immediate slow-wave potentiation due to IASIS session by comparing the voxel-wise Z-score and total abnormal MEG Z-scores between pre- and postsession exams; and 2) assess the between-group treatment effect by comparing IASIS with Sham. The total abnormal MEG Z-score is calculated by summing up the Z-score from all voxels that showed statistically significant slow-wave generation. The dependent variables at both time points are either voxel-wise Z-scores or total abnormal MEG Z-scores, and the predictors are time (pre- and post-session), group (IASIS versus Sham), and their interaction. Veterans receiving IASIS treatment but not sham are expected to show significantly increase rs-MEG slow-wave generation in post-session rs-MEG exam immediately after the treatment session (Hypothesis 2). The preliminary result in C.5 (Fig. 5) supports this hypothesis.

D.4.4. Ultimate slow-wave reduction following the IASIS treatment course -- pre- and post-treatment rs-MEG exams: Participants in mTBI-IASIS group will participate in the 6-week IASIS treatment, whereas those in mTBI-Sham group will participate in a sham treatment for the same time period. To assess the ultimate effect of the IASIS treatment course, the 1-week post-

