- 4) Risk of violation of the right to privacy: subjects' data or diagnostic status could become known by others outside the research team. This is highly unlikely but the possibility is not zero.

Potential Risks from EEG Measurements during IASIS: EEG is a minimal risk procedure. There

are no published risks involved in EEG recording or EEG-biofeedback. Some rubbing alcohol and minimally abrasive preparation gel may be used on skin areas of the face or head for electrode placements. If abrasion is accidentally too strong, there is a slight risk of infection, but because of the high impedance electrodes used here, much less abrasion will be necessary to obtain a clean signal than was necessary with older EEG systems. All instruments will be sterilized between each subject and study staff will thoroughly wash their hands between subjects to diminish any chance of infection. However, because of the 30-min duration of the testing session, subjects may experience some level of unease or discomfort due to the inability to walk around during the session. To avoid such discomfort, we will advise all subjects that if they should feel the need to get up and walk around during the session that they should alert the experimenter immediately and they will be unhooked from the EEG amplifier.

Potential Risks from IASIS Current Neurofeedback Intervention: Temporary side effects are primarily feeling tired, wired (slightly anxious), spacey, lightheaded, or a mild headache. Nausea can also be a temporary side effect. It is possible that some of the participant's current symptoms may very briefly flare up. These side effects are mild and temporary, and last a few minutes to a few hours, occasionally a day and rarely a few days. If participants exhibit any side-effects, they will be monitored for about 15 minutes after the session before being sent home. IASIS treatment does not pose a risk or hazard for operating a motor vehicle. There are no alternative treatments comparable to IASIS that we can provide. The only alternative is not to participate in this study.

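### Hypothesis 2 claims slow-wave potentiation in wakefulness, but no stated step in the MEG pipeline checks, epoch by epoch, that participants were awake

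*Combined protocol and SAP*

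**What the plan says.** Specific Aim 1 (Section 6) makes wakefulness part of the claim. Hypothesis 2 opens: "In wakefulness, slow-wave generation is a signature of ongoing neural rearrangement/healing, rather than a negative consequence of neuronal injury". It then predicts that IASIS raises slow-wave generation right after each session.

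D.4.3 tests this with pre- and post-session scans at Visits 3, 9 and 14, using a time-by-group mixed-design ANOVA. On timing: "The post-treatment rs-MEG will be performed within 30 minutes immediately after the treatment session".

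D.2 says "rs-MEG data will be measured in alert condition" and "The entire recording will have three 5-minute blocks with eyes closed", with one-minute eyes-open breaks between blocks, an instruction to stay alert, and monitoring of blinks and eye movements. Section 15, item 2, adds a live video camera in the MEG room, which is not recorded, and a two-way intercom.

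D.3.1 removes external interference and eye and cardiac artefacts, cuts the data into 2.5-second epochs and band-passes them at 1-4 Hz. Then "the final sensor-waveform covariance matrix is obtained by averaging the covariance matrices across individual epochs for the total 15-minute data". No vigilance step appears there, and the D.7 covariate list has no sleepiness measure.

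Three other statements bear on the point:

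- B.2 says that "during non-REM sleep stages 3 and 4, delta-waves are the dominant brain rhythm in the brain".
- Section 14 says of IASIS: "Temporary side effects are primarily feeling tired, wired (slightly anxious), spacey, lightheaded, or a mild headache", with a usual duration of minutes to hours.
- D.4.2 says that sham sends no pulses.

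**The concern.** The 1-4 Hz measure carries the meaning that Hypothesis 2 gives it only if the participant is awake, because the protocol itself names the same band as the main rhythm of deep non-REM sleep. The recording is 15 minutes with eyes closed, soon after a procedure that can cause tiredness, and every epoch counts equally.

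The sham arm has the same electrode preparation and visit schedule, so it balances fatigue from sitting through a session. It does not balance tiredness caused by the pulses, because sham has none. An arm-specific rise in drowsiness would load on the same time-by-group term as the effect of interest.

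The inference at stake is a central one. Section 6 presents the choice between slow waves as healing and slow waves as a consequence of injury as a fundamental question. The planned test, as written, cannot separate waking potentiation from a change in vigilance.

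**Working it through.** **1. The plan's own figure.** D.8 gives power above 0.98 for Hypotheses 2 and 3 with Cohen's f above 0.45, two-tailed alpha 0.01 and 50 per arm.

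- Simple two-group reading, d = 2f = 0.90: power 0.968 (noncentral t, 98 df).
- Time-by-group reading, λ = f²·N·m/(1−ρ) with N = 100 and m = 2: at least 0.9998 for ρ from 0 to 0.75.

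The stated figure is consistent with the second reading. Nothing here disputes it.

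**2. How much data enter unscreened.** 15 × 60 / 2.5 = 360 epochs per full recording, all averaged.

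**3. Overlap in time.** Listed side effects last minutes to hours, and the scan falls within 30 minutes of the session. The windows overlap.

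**4. Smallest significant difference.** For a two-group comparison of change, critical d = t(0.995; 98 df) × √(2/50) = 0.525. A true shift of this size would be significant about half the time.

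**5. Illustration on the log-magnitude scale.** The documents give no drowsy share, no drowsy-to-awake delta power ratio and no SD of change, so all three are assumed. Let k be the power ratio, and let the drowsy share rise from f0 to f1 in the IASIS arm only.

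- Averaged power ratio = (1 + f1(k−1)) / (1 + f0(k−1)).
- D.3.2 log-transforms source magnitude. Taking magnitude as the square root of power, the shift is 0.5 × ln(power ratio).

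| Drowsy share, pre to post | k | Power ratio | Log-magnitude shift |
|---|---|---|---|
| 5% to 15% | 2 | 1.15/1.05 = 1.095 | 0.045 |
| 5% to 15% | 4 | 1.45/1.15 = 1.261 | 0.116 |
| 5% to 15% | 10 | 2.35/1.45 = 1.621 | 0.241 |
| 5% to 30% | 2 | 1.30/1.05 = 1.238 | 0.107 |
| 5% to 30% | 4 | 1.90/1.15 = 1.652 | 0.251 |
| 5% to 30% | 10 | 3.70/1.45 = 2.552 | 0.468 |

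The shift needed is 0.525 × SD:

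- SD 0.2: 0.105. Five of six scenarios reach it, one of them barely (0.107).
- SD 0.3: 0.158. Three of six reach it.
- SD 0.5: 0.263. One of six reaches it.

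**6. Reaching the full planned effect (d = 0.90).** With no drowsiness before the session, the share needed afterwards is p = (exp(2 × 0.90 × SD) − 1)/(k − 1). That is 24% for k = 4 and SD 0.3. For k = 2 and SD 0.5 it is 146%, which is impossible.

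So drowsiness alone could produce a significant result under some assumed settings and not under others. The total abnormal Z-score, a sum over significant voxels, does not map directly onto this scale.

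**The case against.** The case on the other side has real weight.

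- **Safeguards exist.** A reader might infer that the instruction to stay alert is the only protection. It is not: D.2 and Section 15 also give an alert condition, eyes-open breaks, eye monitoring, live video and an intercom. What remains is that none of these is described as scoring epochs or selecting data, and the video is not kept.
- **Cited methods.** D.2 and D.3.1 refer to published papers for procedure, and these cannot be checked here. The finding is limited to what the protocol text states.
- **Side effects point both ways.** Section 14 lists feeling wired next to feeling tired and gives no frequencies. C.6 reports no side effects in six treated pilot participants with mTBI. The direction and frequency of any vigilance change are therefore unknown.
- **The pilot map is not evidence of sleep.** C.5 says of one healthy control's post-session map: "These areas closely match the known brain networks observed during delta-wave sleep". A reader might infer that this person fell asleep. C.5 states that all three exams were in wakefulness, and B.3 links waking delta to plasticity, so the resemblance fits either account.
- **Light drowsiness is not deep sleep.** B.2 speaks of stages 3 and 4. No figure in the documents supports any particular k for drowsy epochs.
- **Restricting to awake epochs has its own risk.** It selects on a state measured after treatment. A rule based on loss of 8-12 Hz activity could also discard real signal, since B.2 contrasts normal activity above 8 Hz with injury-related slow waves. This argues for a sensitivity analysis rather than a new primary analysis.

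**Conclusion.** The concern holds as a limit on interpretation. The protocol states no step that verifies wakefulness per epoch, and pulse-related drowsiness could contribute to the IASIS-by-time contrast, which the sham arm does not rule out. Its size and direction cannot be computed from the documents; the illustration shows only that it need not be negligible.

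Two stronger readings are tempting, and the documents support neither. The first is that a positive Hypothesis 2 result would be sedation: nothing shows that pulse-specific drowsiness occurs at the scans. The second is that Hypotheses 3 and 6 are biased in the same way. Visit 15 is a week after the last session, largely outside the usual minutes-to-hours window, and the alternative route, in which better sleep makes participants less drowsy at Visit 15, is conjecture.

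This should be fixed before Hypothesis 2 is reported as an effect in wakefulness. It does not invalidate the design or the stated power.

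**What to change.** Add to D.3.1 and D.4.3, before the Hypothesis 2 contrast is interpreted:

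1. For the stored pre- and post-session recordings at Visits 3, 9 and 14 in both mTBI arms, classify each 2.5-second epoch as awake or drowsy/asleep with an automated rule, run blind to arm and visit, that does not use the 1-4 Hz band. Posterior 8-12 Hz power and the monitored eye signals are candidates.
2. Report the drowsy fraction by arm and time point.
3. Repeat the time-by-group analysis on awake epochs only, with epoch numbers equalised within each pre/post pair, as a pre-specified sensitivity analysis beside the all-epoch result.
4. Describe a positive result as potentiation in wakefulness only if the awake-epoch analysis is consistent with it. Otherwise report a post-session rise in delta activity of undetermined state.

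Applying the same check to Hypotheses 3 and 6 is optional and exploratory.

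Cost: re-processing of recordings that Section 27 says are already stored, with no new visits or staff. Section 20 says that visits stopped on 09/30/2022, so sleepiness ratings at the scan can no longer be added. Images will be noisier in participants with few awake epochs. The sample size and the D.8 power calculation do not change.

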
D.3.3. Tasks to evaluate the normative database: We will examine the properties of the HC normative database: 1) to study the database's behavior for deep sub-cortical versus cortical areas; 2) to identify the voxels in the database that meet the requirement of a Gaussian distribution; 3) to test the database's sensitivity to spatial smoothing factors; 4) to assess the database's false-positive rate (i.e., specificity exam) by testing MEG data using the k-fold

validation test (see below); 5) to study a non-parametric approach based on bootstrapping, to expand our approach to voxels that do not meet the Gaussian distribution; 6) to examine the test-retest reliability of the normative database using repeated measures from a subset (N=25) HC Veterans.

D.3.4. Determining the optimal threshold for Zcmax or other MEG measures, and assessing the specificity

(true-negative rate) of MEG slow-wave source imaging: We will examine a variety of thresholds for Zcmax or other MEG measures: 1) For each threshold value, we will assess the specificity of Zcmax or other MEG measures using the k-fold cross-validation method. The k results from the folds can then be averaged (or otherwise combined) to produce a single estimation. 2) For each threshold value, we will assess the number of TBI subjects showing above threshold MEG slow-waves in terms of Zcmax or other MEG measures. Optimal threshold for sensitivity-specificity will be determined using the Youden's index [103] and/or the ROC curves.

D.3.5. Detecting single-subject-basis abnormal MEG slow-waves in mTBI: In mTBI groups, we will apply a voxel-wise approach to identify areas with abnormal MEG slow-wave on a single-subject basis [1]. First, the rs- MEG data in each patient will be processed following the same above Steps 1-2, 5-6, and 8 in D.3.2. Sensitivity assessment of Zc in individual Veterans will be performed in mTBI groups to identify the loci that generate abnormal slow-waves [1] (Fig. 3). The positive detection rate of MEG slow-wave source imaging will be assessed using the Zcmax (see Fig. 2). Since the brain areas injured by TBI are highly heterogeneous across individuals, and often without a global effect, using the Zcmax value across the whole brain is equivalent to examining the hypothesis that at least one region shows abnormal slow-waves.

D.3.6. Assessing the sensitivity and specificity values in mTBI: conventional MRI versus MEG slow-wave: MRIs will be reviewed by a Board certified neuroradiologist ([name]) to determine if the participants have visible lesions. An MRI diagnostic variable of sensitivity (positive detection rate) will be created with "Y" for participants in mTBI and HC groups showing abnormal MRI finding(s) and "N" for the ones with normal results. Participants with visible ventricular dilation or ventricular asymmetry will be excluded from the HC group. T2-weight hyperintensities may or may not be associated with mTBI. Incidental age-related T2-weighted hyperintensities may show in some healthy participants without any association with head injury. Therefore, only Veterans with beyond age-appropriate T2-weighted hyperintensities will be considered positive in the HC group. In mTBI groups, participants with visible lesions, ventricular dilation, ventricular asymmetry, or beyond age-appropriate T2-weighted hyperintensities will be considered as positive MRI findings. In our experience, only in rare cases do HC subjects show some beyond age-appropriate hyperintensities in T2-weighted MRI. Otherwise, MRI in HC group will be negative. Therefore, the MRI specificity will be greater than 90%.

